## 5. GENERAL METHODOLOGY AND CONVENTIONS

[figure not shown]
### 5.1. Hypotheses and Decision Rules

#### 5.1.1. Hypotheses and Sample Size

##### 5.1.1.1. Phase 1b

The primary objective in the Phase 1b part of the study is to assess safety and tolerability of PF-06863135 in combination with the combination partner agent in order to select a RP2D for the combination therapy. There is no statistical hypothesis for the Phase 1b part of the study. A BLRM will be utilized for dose escalation of PF-06863135.

CCI

#### Sample Size Estimation

A minimum of 2-6 DLT-evaluable participants (as defined in [Section 4](#)) will be treated at each dose level of PF-06863135. The actual number of participants to be enrolled will depend on the number of dose levels evaluated and the number of participants treated at each dose level in each sub-study. Therefore, it cannot be determined in advance.

For sub-study A, it is estimated that approximately 21-24 DLT evaluable participants will be enrolled and treated with PF-06863135 combination which will include at least 6 DLT evaluable participants treated at the PF-06863135 combination MTD/MAD level and at least 9 DLT evaluable participants at the PF-06863135 combination RP2D level.

If any participant is deemed non-evaluable for DLT, additional participants may be enrolled to ensure there are a sufficient number of evaluable participants in the Phase 1b of each sub-study.

### **5.1.1.2. Phase 2**

The primary endpoint in the Phase 2 part of the study is ORR per IMWG response criteria as determined by investigator. No hypothesis significance testing will be performed. Instead a Bayesian dual-criterion design will be used to estimate the true ORR of PF-06863135 in combination with the combination partner agent. With this design, the following criteria are defined:

- Bayesian statistical significance: Substantial evidence that the true ORR exceeds a null value. For the PF-06863135 combination therapies, Bayesian statistical significance will be achieved if the posterior probability of the true ORR  $\geq 65\%$  exceeds 0.95;
- Clinical relevance: The minimum ORR threshold that could justify further development of a combination. For the PF-06863135 combination therapies, it is defined as the median of the posterior distribution of the true ORR exceeding 75%.

The analysis will use a Beta-binomial model (binomial sampling for number of responders and a Beta prior distribution). A minimally informative beta prior distribution of the true ORR will be used. It is assumed a priori that the true mean ORR for a combination is 65%, so the prior distribution will be Beta (1.3, 0.7). Using this prior and based on the dual criteria defined above, approximately 50 participants will be enrolled in the Phase 2 part of each sub-study and a minimum of 38 objective responses are required to achieve the dual criteria in 50 participants. With exactly 38 objective responses in 50 participants, the observed ORR is 76% with median 75.9% and 90% credible interval of (65.3%, 84.7%) based on the posterior distribution.

### **5.1.2. Decision Rules (all Sub-studies)**

#### **5.1.2.1. Phase 1b**

##### **Identification of MTD/MAD**

[figure not shown]
The dosing decision and estimation of the MTD/MAD for each combination will be guided by the estimation of the probability of DLT during the DLT observation period. Other evidence such as safety data beyond DLT window, clinical activity, PK, and PD data will also be evaluated in determining RP2D.

### **Assessment of Participant Risk**

After each dosing cohort of participants completes the DLT observation period, the posterior distribution for the risk of DLT for each dose combination will be evaluated. The posterior distributions will be summarized to provide the posterior probability that the risk of DLT lies within the following intervals.

- Underdosing: [0, 0.16);
- Target toxicity: [0.16, 0.33);
- Excessive toxicity: [0.33, 1].

CCI

#### **5.1.2.2. Phase 2**

The Part 2 of each sub-study is designed to have an interim analysis for futility and a primary analysis. The interim analysis will be conducted after the first 25 participants are treated and followed for at least 2 post-baseline disease assessments in each sub-study. The primary analysis will be conducted once all participants have been followed for response for at least 6 months or have otherwise discontinued response assessments within the first 6 months of treatment.

[Table 2](#) presents the operating characteristics of this 2-stage design, ie, the probability of early trial termination at the interim futility analysis and the probability of observing the critical number of objective responses (ie,  $\geq 38$  objective responses in 50 participants) at the primary analysis if the true ORR ranges from 65% to 90%. Specifically,

- If the true ORR = 65%, the probability of stopping the study due to futility at the interim analysis is 0.533, and the probability of observing critical number of responses at the primary analysis is 0.064.
- If the true ORR = 80%, the probability of stopping the study due to futility at the interim analysis is 0.047, and the probability of observing critical number of responses at the primary analysis is 0.806.

**Table 2. Operating Characteristics of Bayesian 2-Stage Dual-Criterion Design**

True ORR	Prob of Exceeding Futility Boundary at the Interim (R1/N1 <17/25)	Prob of GO Decision at the Primary Analysis* (R/N ≥38/50)	Prob of No-GO Decision at the Primary Analysis* (R/N <38/50)
65%	0.533	0.064	0.403
70%	0.323	0.218	0.459
75%	0.149	0.502	0.349
80%	0.047	0.806	0.147
85%	0.008	0.967	0.025
90%	<0.001	0.999	0.001

\* The study does not meet futility criteria at the interim analysis and continues to the primary analysis.

ORR = objective response rate;

R1 = Minimum number of responses required at the interim futility analysis to continue the study;

N1 = Number of participants at the interim analysis;

R = Minimum number of responses required to meet the dual criteria at the primary analysis;

N = Number of participants at the primary analysis.

At the time of the primary analysis, the critical number of objective responses to be observed will be updated based on the actual number of participants enrolled and treated.

Meeting the dual criteria described above will be considered preliminary evidence that the combination therapy may provide clinically meaningful treatment effect in ORR. However, the decision as to whether a combination will be developed further will depend upon the observed results of both the primary and key secondary efficacy endpoints. As a result, exceeding the critical number of objective responses described above may be sufficient, but may not be necessary, for justifying further development of a combination therapy.

## 5.2. General Methods

Unless otherwise specified, all analyses will be performed for Phase 1b and Phase 2 separately and with the cohort of RP2D in Phase 1b and Phase 2 combined.

For the Phase 1b part of the study, all analyses will be performed by dose level and with all dose levels combined. For sub-study A, participants on Dose levels 1 and 2 escalated to the next higher dose level(s) will be summarized with the dose level originally assigned.

### 5.2.1. Data Handling After the Cutoff Date

Data after the cutoff date may not undergo the cleaning process and will not be displayed in any listings or used for summary statistics, statistical analyses or imputations.

### 5.2.2. Pooling of Centers

In order to provide overall estimates of treatment effects, data will be pooled across centers. The ‘center’ factor will not be considered in statistical models or for subgroup analyses due to the high number of participating centers in contrast to the anticipated small number of participants randomized at each center.

### 5.2.3. Analyses to Assess the Impact of COVID-19 Pandemic

The study enrollment may start during the COVID-19 pandemic period. If so, data summaries and analyses may be performed to assess the impact of COVID-19 on the trial population and study data. Details of these summaries and analyses are included in the respective sections.

### 5.2.4. Definition of Study Day

The study day for assessments occurring on or after the first dose of study intervention (eg, adverse event onset, disease measurement) will be calculated as:

$$\text{Study day} = \text{Date of the assessment/event} - \text{start date of study intervention} + 1.$$

The study day for assessments occurring prior to the first dose of study intervention (eg, baseline characteristics, medical history) will be negative and calculated as:

$$\text{Study day} = \text{Date of the assessment/event} - \text{start date of study intervention}.$$

The study day will be displayed in all relevant data listings.

### 5.2.5. Definition of Cycle and Cycle Day

Cycle start and end dates are derived per participant. The definition for each cycle is driven by study intervention PF-06863135.

The first cycle of PF-06863135 is 35 days from Cycle 0 Day 1 through Cycle 1 Day 28 (the 1-week period after the priming dose of PF-06863135 on Cycle 0 Day 1, plus 4 weeks of combination study intervention that begins on Cycle 1 Day 1). Starting from Cycle 2, PF-06863135 is administered on Days 1, 8, 15 and 22 of each 28-day cycle. As described in Section 12.5.2 of the protocol, if a participant has received QW dosing for at least 6 cycles and has achieved an IMWG response category of PR or better persisting for at least 2 months, the dosing interval will be changed from QW to Q2W. If the participant subsequently begins to have an increase of disease burden not yet qualifying as PD according to IMWG criteria, dose intervals should return to weekly dosing. If the dose interval is changed, cycles should remain the same length (ie, 4-week cycles). In either dosing scenario, the nominal cycle length is 28 days (except Cycle 1 is 35 days).

- For Cycle X, the actual cycle start date for each participant is the earliest start date of dosing in the Cycle X Day 1 visit CRF exposure page, if the participant received study intervention on that visit (ie, any study drug with dose >0 at that visit).

- For all but the last cycle:
  - Actual cycle stop date is calculated as the start date of the next cycle minus 1 day;
  - Actual cycle duration is calculated from Day 1 of a cycle to the day prior to Day 1 of the next cycle, as follows:
    - Actual Cycle Duration (weeks) = (cycle stop date – cycle start date + 1)/7.

For the last cycle, actual cycle duration is the planned cycle duration and actual cycle stop date is calculated as actual cycle start date + 28 – 1 day.

The cycle day will be calculated as:

$$\text{Cycle day} = \text{Date of the assessment/event} - \text{cycle start date} + 1.$$

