### **Dose Delay**

Section 12.10.2 in the protocol specifies that if PF-06863135 cannot be administered on the planned day, it should be skipped until the next planned dose (ie, if Day 15 dose cannot be administered, the dose should be skipped until Day 22). Therefore, dose delay is not applicable to PF-06863135 per protocol.

Dose delay is not applicable to nirogacestat (sub-study A).

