**Table 2. Study Intervention Dose Levels and Administration**

Dose Levels (DL)	Elranatamab	Nirogacestat
1 (starting dose level)	Priming Dose: 4 mg C0D1 SC Full Dose: 4 mg C1D1 SC, weekly thereafter b	100 mg PO BID continuous starting on C1D1 until response a
2	2 Step-up Priming Dose: 4 mg C0D1 SC / 8 mg C0D4 SC Full Dose: 12 mg C1D1 SC, weekly thereafter b	100 mg PO BID continuous starting on C1D1 until response a
3	2 Step-up Priming Dose: 12 mg C0D1 SC / 32 mg C0D4 SC Full Dose: 32 mg C1D1 SC, weekly thereafter b	100 mg PO BID continuous starting on C1D1 until response a
Nirogacestat De-Escalation Levels		
3A	2 Step-up Priming Dose: 12 mg C0D1 SC / 32 mg C0D4 SC Full Dose: 32 mg C1D1 SC, weekly thereafter b	100 mg PO QD continuous starting on C1D1 until response a
4A	2 Step-up Priming Dose: 12 mg C0D1 SC / 32 mg C0D4 SC Full Dose: 76 mg C1D1 SC, weekly thereafter b,c	100 mg PO QD continuous starting on C1D1 until response a
3B	2 Step-up Priming Dose: 12 mg C0D1 SC / 32 mg C0D4 SC Full Dose: 32 mg C1D1 SC, weekly thereafter b	50 mg PO QD continuous starting on C1D1 until response a
4B	2 Step-up Priming Dose: 12 mg C0D1 SC / 32 mg C0D4 SC Full Dose: 76 mg C1D1 SC, weekly thereafter b,c	50 mg PO QD continuous starting on C1D1 until response a

- a. For Dose levels 3A/3B and 4A/4B, nirogacestat will be adjusted to 50 mg QD continuous at time of confirmed VGPR. Once CR (or better) is confirmed, nirogacestat will be permanently discontinued. For all other dose levels, nirogacestat can be continued or adjusted based on this guidance, per investigator discretion. See Section 6.1.1.5.
- b. Starting at Cycle 7, if a participant has received QW dosing for at least 6 cycles and PR or better persisting for ≥2 months, dose interval will be changed from QW to Q2W. See Schedule of Activities.
- c. For participants on Dose levels 4A and 4B receiving CCI dosing, CCI the dose interval will be changed to CCI

090177e1a0f4f44c\Approved\Approved On: 14-Jun-2024 22:12 (GMT)

CCI

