#### 6.6.3.1. Exposure to Elranatamab

The summary of treatment exposure to elranatamab will include the following information:

- Treatment duration (weeks);
- Number of cycles started per participant (mean, median, min, max);

- Number and percent of participants starting a cycle (any cycle, cycle 0, 1, 2, 3, 4, 5, 6, 7, 8, 9, 10, 11, >=12 cycles);
- Total cumulative dose (mg);
- Overall dose intensity (mg/week);
- Overall relative dose (%);
- Overall relative dose intensity (%);
- Number and percent of participants after 6 cycles who switched from QW to Q2W;

CCI

The treatment duration of elranatamab (in weeks) during the study for a participant is defined as:

$$\text{Treatment duration (weeks)} = (\text{last dose date} - \text{first dose date} + 1)/7$$

Planned treatment duration and intended treatment duration are needed to calculate dose intensity (DI) and relative dose intensity (RDI). It is defined as follows:

- Planned treatment duration (weeks) = 1 (1 week for Cycle 0) + number of cycles started  $\times$  4 - (number of weeks in the last cycle after permanent treatment discontinuation or data cutoff for those on-treatment).

Intended treatment duration (weeks) = (last zero/non-zero dose date – first dose date)/7 + ( 1 if on QW or 2 if on Q2W CCI ). If C0D4 is the last visit, duration is 1 week if C0D4 occurred by then; The planned dose for a given cycle is defined as:

- Cycle 0:
  - Planned dose (mg/cycle) = Planned priming dose(s) per protocol during C0
- After Cycle 0:
  - If the participant is on QW dosing schedule for the cycle:  
Planned dose (mg/cycle) = Full dose  $\times$  4
  - If the participant is on Q2W dosing schedule for the cycle:  
Planned dose (mg/cycle) = Full dose  $\times$  2

CCI

**Note:** Full dose= 4 ,12, 32, or 76mg depending on DLs. For the last cycle, subtract planned doses after a participant permanently discontinues treatment or data cutoff for those on-treatment.

Total planned dose is the sum of the total planned dose across all cycles.

The total cumulative dose (mg) of elranatamab is the sum of the actual doses that the participant received during the study; the cumulative dose (mg) of elranatamab per cycle is the sum of the actual doses that the participant received within that cycle (ie, total dose administered [mg]).

The DI, relative dose (RD), and the RDI will be calculated for each participant across all cycles and also for each individual cycle:

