The total cumulative dose (mg) of elranatamab is the sum of the actual doses that the participant received during the study; the cumulative dose (mg) of elranatamab per cycle is the sum of the actual doses that the participant received within that cycle (ie, total dose administered [mg]).

The overall DI, relative dose (RD), and the RDI will be calculated for each participant across all cycles and also for each individual cycle:

- Overall DI (mg/week) = Total cumulative dose (mg)/Intended treatment duration (weeks);
- Overall planned DI (mg/week) = Total planned dose (mg)/ Planned treatment duration (weeks);
- Cycle DI (mg/week) = Cumulative dose for a given cycle (mg)/actual cycle duration (in weeks);
- Cycle Planned DI (mg/week) = Total planned dose for a given cycle (mg)/4 weeks.

The RD and RDI are defined as follows:

- Cycle RD (%) = Total given dose for a given cycle (mg) /Total planned dose for a given cycle (mg) × 100;
- Overall RD (%) = Total cumulative dose (mg) /Total planned dose (mg) × 100;

- Cycle RDI (%) = Cycle DI (mg/week) /Cycle Planned DI (mg/week) × 100;
- Overall RDI (%) = Overall DI (mg/week) /Overall Planned DI (mg/week) × 100.

Cycle DI and Cycle RDI will be summarized and plotted vs time (weeks).

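### A cycle with no drug given on Day 1 has no start date, which distorts cycle RDI and can push overall relative dose above 100%

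*SAP*

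**What the plan says.** - **Start of a cycle.** Master SAP 5.2.5 takes the start of Cycle X from the Day 1 exposure page, "if the participant received study intervention on that visit (ie, any study drug with dose >0 at that visit". The same section opens by saying "The definition for each cycle is driven by study intervention PF-06863135". Section 5.2 of each sub-study SAP refers back to Section 5.2 of the master SAP for general methods.
- **End of a cycle.** For all but the last cycle, "Actual cycle stop date is calculated as the start date of the next cycle minus 1 day". The last cycle is closed 27 days after its start.
- **Skipped doses.** The Dose Delay text in master SAP 6.6.3.1 says of an elranatamab dose that cannot be given on its planned day that "it should be skipped until the next planned dose".
- **Planned duration.** Sub-study A SAP 6.6.3.1: "Planned treatment duration (weeks) = 1 (1 week for Cycle 0) + number of cycles started", the count being multiplied by 4 and reduced for weeks after permanent discontinuation or data cutoff.
- **Planned dose.** Same section: "Total planned dose is the sum of the total planned dose across all cycles".
- **Cycle-level measures.** Master SAP 6.6.3 and Sub-study B SAP 6.6.3.1 divide the dose in a cycle by the actual cycle duration to obtain cycle DI, and divide planned dose by 4 weeks to obtain planned cycle DI. Sub-study B adds "Cycle RD (%) = Total given dose for a given cycle (mg) /Total planned dose for a given cycle (mg". Sub-study A asks for cycle DI and cycle RDI without restating the formulas.
- **Stopping the partner.** Sub-study A SAP Table 2, footnote a, for dose levels 3A/3B and 4A/4B: "Once CR (or better) is confirmed, nirogacestat will be permanently discontinued".

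**The concern.** The start-date rule covers only cycles that were dosed on Day 1. A participant can miss everything on Day 1 and be dosed on Days 8, 15 and 22. That cycle then has no start date, no stop date and no duration, and the previous cycle runs on to the next dated one.

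The number of cycles started is a reported output and an input to planned duration, but no SAP defines it. Section 5.2.5 holds the only cycle-start rule, so a programmer may well count only dated cycles.

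Cycle RDI, cycle relative dose, overall relative dose and the number of cycles started are prespecified exposure summaries for a combination whose tolerability is under study. They could be wrong in either direction, and two programmers could produce different tables from the same data.

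**Working it through.** The SAPs state no relative dose or RDI value to reproduce. The one worked planned-dose figure, nirogacestat in Sub-study A SAP 6.1.1, is 100 × 2 × 28 = 5600 mg and reproduces exactly.

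**Inputs.** Sub-study A dose level 4A/4B (Table 2): priming 12 + 32 = 44 mg, then 76 mg weekly, four doses per 28-day cycle. Assumed: six weekly cycles, nothing given on C3D1 (nirogacestat also at 0 mg or already stopped), all other elranatamab doses given.

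**Cycle level, from the stated rules alone.** Cycle 3 is undated, so Cycle 2 runs from C2D1 to the day before C4D1, which is 8 weeks. Planned cycle DI = 4 × 76 / 4 = 76 mg/week.
- Doses assigned by date: Cycle 2 holds 4 + 3 = 7 doses. Cycle DI = 7 × 76 / 8 = 66.5 mg/week; RDI = 66.5 / 76 = 87.5%.
- Doses assigned by CRF label: Cycle 2 holds its own 4 doses. Cycle DI = 4 × 76 / 8 = 38 mg/week; RDI = 50%.
- Sub-study B cycle relative dose, by date: 7 × 76 / (4 × 76) = 175%.
- Cycle 2 was in fact fully dosed, so the correct value of each is 100%.
- If the undated cycle is the final one, the cycle before it closes 27 days after its start and the later doses belong to no cycle.

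**Overall relative dose (RD = given / planned), if the undated cycle is dropped from planned dose.**
- Given: 44 + 23 × 76 = 1792 mg.
- Planned, all six cycles: 44 + 24 × 76 = 1868 mg; RD = 1792 / 1868 = 95.9%.
- Planned, undated cycle dropped: 44 + 20 × 76 = 1564 mg; RD = 1792 / 1564 = 114.6%.
- All four doses of that cycle held: given 1564 mg; RD = 1564 / 1564 = 100.0%, instead of 1564 / 1868 = 83.7%.

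Varying the assumed number of weekly cycles, one undosed Day 1:

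| Cycles | RD, all cycles | RD, undated cycle dropped |
|---|---|---|
| 3 | 92.1% | 135.0% |
| 4 | 94.0% | 123.8% |
| 6 | 95.9% | 114.6% |
| 12 | 97.9% | 106.7% |

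With six weekly then six two-weekly cycles and one undosed Day 1 in the two-weekly period, RD is 2704 / 2628 = 102.9%, instead of 2704 / 2780 = 97.3%.

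**Overall RDI.** Intended duration uses calendar dates and is 25 weeks, so DI = 1792 / 25 = 71.68 mg/week.
- All cycles: planned DI = 1868 / 25 = 74.72; RDI = 95.9%.
- Undated cycle dropped from both dose and duration: planned DI = 1564 / 21 = 74.48; RDI = 96.2%. Planned dose and planned duration shrink together.
- Planned dose over all six cycles but duration over dated cycles only: planned DI = 1868 / 21 = 88.95; RDI = 80.6%. Overall RDI is therefore stable only if both use the same set of cycles.

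**The case against.** **One held dose does not trigger this.** A reader might infer that any held elranatamab Day 1 removes the cycle, especially from the opening sentence that makes elranatamab the driver. The bullet that sets the date accepts any study drug. Nirogacestat is continuous from C1D1 until it is adjusted or stopped for response, and lenalidomide is planned on Day 1 of every cycle. While the partner is taken that day, the cycle is dated. This stands, and it makes the case uncommon. It does not remove it: at dose levels 3A/3B and 4A/4B, elranatamab becomes the only drug by design after confirmed CR.

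**Dropping the cycle from planned dose is an inference.** Planned dose is summed over all cycles, not dated cycles. Master SAP 5.2.11 uses CRF visit labels as the nominal timepoint, and Sub-study A SAP 6.1.1 uses nominal cycle length for nirogacestat in the DLT period. On that reading RD is 95.9%. This also stands, so 114.6% is conditional. CRF labels do not repair the cycle-level result, because the 8-week duration comes from the dates; assignment by label gives the 50%.

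**The skip rule is older text.** The master SAP says delay does not apply to elranatamab, whereas both later sub-study SAPs define delay categories. Those passages need reconciling. A late dose recorded on the Day 1 page still starts the cycle. Missed doses remain possible, since both sub-study SAPs define interruptions.

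**Under-dosing is not hidden.** Interruptions are counted directly, including those due to AEs (Sub-study A SAP 6.6.3.3, Sub-study B SAP 6.6.3.4). Sub-study A SAP 5.1.2.1 does not name relative dose among the inputs to the RP2D. A reader who inferred concealment, or an effect on dose selection, would go beyond the documents.

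**Conclusion.** The gap is real and narrow. An undosed Day 1 has no fallback, and the stated rules then misreport a fully dosed preceding cycle: RDI of 87.5% or 50%, and a Sub-study B cycle relative dose of 175% if doses are assigned by date. That result needs no inference beyond how doses are assigned to cycles.

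The overall figures of 114.6% (instead of 95.9%) and 100.0% (instead of 83.7%) further assume that the undated cycle is left out of planned dose. The SAPs neither require nor exclude this. They also rest on the assumed six weekly cycles; with one undosed Day 1 and 3 to 12 weekly cycles, RD runs from 135.0% down to 106.7%.

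The documents give no rate for a Day 1 on which every drug is at 0 mg or stopped, so no share of affected participants can be stated. Only descriptive exposure summaries are touched.

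**What to change.** - In master SAP 5.2.5, set the start of Cycle X to the Day 1 dosing date; if nothing was given on Day 1, to the date of the Day 1 visit (0 mg record); otherwise to the previous cycle start + 28 days.
- Define a cycle as started by its CRF cycle label, for every cycle between first dose and permanent discontinuation or data cutoff. Include cycles in which every dose was held; a rule requiring at least one dose would leave the 100.0% instead of 83.7% error in place.
- Use that same set of cycles for planned dose, planned duration and cycle duration in all three SAPs.
- Make the opening sentence of 5.2.5 and its start-date bullet agree on which drug drives the cycle.

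The cost is one SAP definition and a small programming change. Zero-dose dates are already used for intended duration, so new data collection should not be needed. Some relative dose figures will be lower than under a dated-cycles-only count.
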